MH Group: CHWs will carefully explain participants the sequence of SMS messages to be received depending on the Test results, and how they should proceed after reception of the SMS messages. If the woman does not have a personal phone, she will be asked if she is willing to be contacted and receive the proposed SMS messages on a shared phone. CHWs will inform women about the nature and content of the SMS messages to be received. They will also explain that they might come back for a personal visit if they have not performed triage 60 days after the test results. Therefore, consent to participate also means women agreement to be contacted and receiving SMS messages, even if phones are shared by several family members.

Women with positive self-collected tests will receive a multi-component intervention (Figure 1). Upon registration in SITAM of the HPV result at the laboratory, they will receive a weekly SMS message for four weeks, notifying them that the test results are available, and they should go to the health center. Messages will be stopped if a Pap result is registered in SITAM.

Sixty days after the date of the Test result, CHWs will receive an e-mail and SMS message informing them that there are HPV+ women who have not had Pap triage (if this is the case). The e-mail will also contain a secure link to the list of HPV+ women to be visited, as explained above. CHWs will be asked to confirm receipt of the e-mail for monitoring project processes. CHWs will visit these HPV+ women within 15 days of being notified, for an in-person reminder and counseling about the importance of attending health centers and have triage performed. The script for this visit will be developed based on the results of the FGD using HBM concepts to address issues of perceived susceptibility, perceived severity, and benefits of triage. If possible, CHWs will also provide support to address barriers (e.g., connecting women with transport available in some municipalities). We will track CHW visit information on the Trial form, including visit attempts, date of visit and issues addressed during counseling. The subgroup of HPV+ women visited by CHWs are given 30 days to

get screened as we consider that they are probably women facing specific obstacles (i.e. lack of transportation) and might need additional time to solve them. This timeline is in agreement with programmatic organization of the cervical cancer prevention process.

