(see Analysis Plan below). In addition, a larger number of CHWs in the intervention group will benefit the assessment of the implementation outcomes. Based on PHC records and previous experience¹⁴ we estimate that each CHW will enroll an average of 20 eligible women in a 10-month period. We assumed an attrition rate of 20% due to problems with mobile phones (i.e. non-identified number, unpaid phone bill, lack of signal, etc.), SMS messages not delivered and/or other issues. Under a 13% prevalence of HPV+ in this population,¹¹ we estimate that each CWH will contribute with an average of 2 HPV+ women. **Primary outcome:** The target sample size (120 CHWs in the MH group and 80 CHWs in the UC group, each one providing 2 HPV+ women) will have 97% power to detect a 20% triage difference between the two groups when the control group has a 30% triage in a 120-days period (two-sided test, alpha=0.05). Correlation induced by the CHWs was included in power calculations assuming an intra-class correlation coefficient of 0.10. **Secondary outcome:** Under the same assumptions, the proposed sample size will have 90% power to detect a difference of 10% in triage between groups when the control group has a 15% triage by day 60.

A specifically built database will be used (RCT database), combining information from the Trial Form, the AS Monitoring Registry, and SITAM, the national screening information system.⁵² The Trial Form will register information about the randomization group, agreement to participate in the study, women's socio-demographic data, and tasks performed by the CHWs (contact after reminder and reasons of no contact). Data on HPV testing, triage, diagnosis and treatment will be uploaded importing data from SITAM, linking the records through each woman's national identification number. The AS Monitoring Registry will include data from the Automated System regarding receipt of confirmatory SMS messages and e-mails, and valid phone numbers and e-mails. Data entry will be done through specific software that will include range and inter-item consistency checks. Data will be stored in files compatible for analysis with statistical packages (Stata).

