Analysis plan: All analysis will be conducted on an intention-to-treat (ITT) basis; the effect of the multi-component mHealth intervention on the primary outcome will be assessed using a generalized estimating equations approach. The model (logit link, and binomial distribution) will include trial group as fixed effect and CHWs as the clustering variable. Potential effect modification due to rural/urban location of the woman and CHW gender will be evaluated. Baseline socio-demographic characteristics of the women will be compared between groups using the same model with link and distribution selected depending on the variable. Factors showing clear unbalance between arms will be included in the model proposed above to adjust for potential confounding. The same approach will be used to estimate the intervention effect on the secondary outcome. Analyses will be conducted using STATA 14.0 or SAS v.9.4. The trial will follow the CONSORT extension for cluster randomized trials reporting guidelines.⁶³

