Finally, we will carry out a **Structured questionnaire among HPV+ women (Women Survey)** to evaluate their acceptability of the strategy, their perspectives about the implementation, and reasons for adherence and non-adherence to triage. We will survey all HPV+ women from the RCT intervention group (approximately 240 women), 5 months after the HPV test result (this is, one month after measurement of the primary outcome), irrespective of their triage status. The questionnaire will include open and closed questions with dimensions related with women's experiences and

Table 1. Measurements and data sources proposed for Implementation Evaluation based on RE-AIM and CFIR

	Quantitative outcomes	Qualitative evaluation	Data source
Reach Representativeness of women reached by the intervention (quantitative data)	-% of eligible women who accepted to participate in the study -Socio-demographic information of participant/non-participant women		RTC database (Trial Form)
Effectiveness in increasing women's adherence to triage (quantitative and qualitative data)	-Primary outcome: percentage of women with triage smears 120 days after test results are registered in SITAM.	Reasons for adherence/non adherence to triage.	RCT database (SITAM) HPV+ Women Survey
Adoption by CHWs of the strategy of visiting HPV+ women after receiving SMS messages and e-mails*	-% of CHWs that visited at least one HPV+ women after receiving the SMS message and e-mail.		RCT database (Trial Form+Automated System Monitoring Registry)
Acceptability of the intervention by adopters	-% of CHWs that agreed with programmatic incorporation of the mHealth intervention.	CFIR construct: Knowledge and beliefs about the intervention; perceived self-efficacy	Self-administered semi-structured survey of CHWs
Implementation of intervention activities according to protocol (quantitative data)	-% of randomized CHWs that participated in trainings. -% of SMS messages that reached a valid phone number. -% of HPV+ women who sent confirmatory SMS messages. -% of e-mails that reached a valid e-mail address. -% of CHWs who sent confirmatory e-mails.		Automated System Monitoring Registry and Training Attendance List

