Acceptability of the intervention by women. (quantitative and qualitative data)	-% of women who accept and are satisfied with the intervention.	Women level Experience and perception of the intervention; acceptability of SMS messages, pertinence of frequency, reception time and content of SMS messages.	HPV+ Women Survey
Barriers and facilitators to implementing and administering the intervention (qualitative data)		Stakeholder/CHWs level CFIR constructs: Relative Advantage; Adaptability; complexity and cost. Patient Needs & Resources and External Policies & Incentives. Structural Characteristics; Tension for Change; Relative Priority and available Resources, Access to Knowledge & Information.	Semi-structured interviews with stakeholders and Self-administered semi-structured survey of CHWs
Maintenance		Intention to incorporate the strategy.	Interview with Stakeholders

*Adoption of the Automated System will not be measured as it will be a unique centralized system linked to SITAM

perceptions, including acceptability and relevance of SMS message frequency, receipt time, and content; perceived effect of the multiple components of the intervention on their adherence, and reasons for adhering/not adhering to triage. The nominated list of these women and their contact details will be extracted from the RCT database. Trained interviewers will contact these women via telephone to make an appointment to visit them at their homes to administer the questionnaire. The training will be carried out by the project staff; it will include formal aspects regarding applying the questionnaire as well as skills for developing a connection with the interviewees. Interviewers will be provided with a list of women to interview with contact information.

Quantitative data analysis. This section refers to the analysis of data from the Women Survey and the Self-administered semi-structured survey of CHWs. A descriptive analysis of each study dimension will be carried out using simple frequencies and percentages for each of the variables under study. The association between the variables will be measured using the Chi square test of independence. Outcomes will be summarized as percentages and compared across women/CHWs socio-demographic characteristics using logistic regression. Results will be presented as estimates and 95% confidence intervals. Analysis will be conducted using STATA (version 13.0) and/or SAS (version 9.3).

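### The Women Survey analysis ignores clustering by community health worker, so some of its 95% intervals would be slightly too narrow

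*Combined protocol and SAP*

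**What the plan says.** The section headed Quantitative data analysis, under Specific Aim 2, is confined to two data sets: the Women Survey and the self-administered survey of CHWs. After simple frequencies and percentages it specifies three things:

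- For testing association, an unadjusted chi-square test.
- For the survey outcomes, a regression step: "Outcomes will be summarized as percentages and compared across women/CHWs socio-demographic characteristics using logistic regression".
- For reporting, point estimates with 95% confidence intervals.

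It mentions no cluster term, generalized estimating equations (GEE), random effect, robust variance or design effect.

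The Women Survey sample is defined in the same Aim: "We will survey all HPV+ women from the RCT intervention group (approximately 240 women"). Under Randomization and sample size calculations there are 120 CHWs in the intervention arm, and "we estimate that each CWH will contribute with an average of 2 HPV+ women". The surveyed women are therefore nested in CHWs, about two to each.

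The Analysis plan for Aim 1 treats the same nesting differently. It uses GEE with the CHW as clustering variable for the primary and secondary outcomes, and adds: "Baseline socio-demographic characteristics of the women will be compared between groups using the same model". The sample size section allows for an ICC of 0.10 for triage.

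**The concern.** The chi-square test, ordinary logistic regression and the usual binomial interval all treat the 240 women as independent. There is reason to expect some similarity among women of one CHW. At enrolment in the intervention arm, "CHWs will carefully explain participants the sequence of SMS messages to be received", and the same CHW is prompted to visit women who have had no triage by day 60. The questionnaire asks about the perceived effect of the intervention components and about reasons for adhering or not, so some items bear on what the CHW did.

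With positive within-CHW correlation, two kinds of result are affected:

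- **Overall percentages.** One is the Table 1 acceptability measure, the percentage "of women who accept and are satisfied with the intervention".
- **Comparisons on characteristics shared by all women of a CHW**, such as CHW gender and, largely, urban or rural setting.

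At stake is the stated precision of the RE-AIM acceptability results. No decision threshold hangs on them.

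**Working it through.** **Inputs from the documents.** 120 intervention CHWs and 80 usual-care CHWs; 2 HPV+ women each (240 and 160 women); ICC 0.10 for triage; 20 women enrolled per CHW, 20% attrition, 13% HPV+ (20 × 0.8 × 0.13 = 2.08 HPV+ women per CHW).

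**Assumed.** ICCs of 0.05 and 0.20 to show a range; use of any of these ICCs for survey items; binomial variation in cluster size.

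**The plan's own figure.** The documents give no precision for the survey, so the check is on the primary-outcome power of 97% for 30% versus 50%.

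- Design effect DE = 1 + (m − 1) × ICC = 1 + (2 − 1) × 0.10 = 1.10.
- Effective sizes are 160/1.10 = 145.5 and 240/1.10 = 218.2. The pooled proportion is 0.42.
- SE under the null = √[0.42 × 0.58 × (1/145.5 + 1/218.2)] = 0.0528.
- SE under the alternative = √[0.21/145.5 + 0.25/218.2] = 0.0509.
- z = (0.20 − 1.96 × 0.0528)/0.0509 = 1.90, so power is 97.1%.

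The stated 97% is reproduced. Without the ICC the result is 98.2%, so the match alone does not prove that clustering was applied, but the text says it was.

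**Overall percentages in the Women Survey.** Narrowing of the interval = 1 − 1/√DE. Coverage = 2Φ(1.96/√DE) − 1. Half-width = 1.96 × √[p(1 − p) × DE/240].

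For unequal clusters, m is replaced by E[m²]/E[m]. With sizes distributed as Binomial(16, 0.13), the mean is 2.08 and the variance 16 × 0.13 × 0.87 = 1.81, so E[m²]/E[m] = 1.81/2.08 + 2.08 = 2.95.

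| Cluster sizes | ICC | DE | Too narrow by | Coverage | Half-width at 50% (naive 6.33) | Half-width at 80% (naive 5.06) |
|---|---|---|---|---|---|---|
| 2 each | 0.05 | 1.05 | 2.4% | 94.4% | 6.48 | 5.19 |
| 2 each | 0.10 | 1.10 | 4.7% | 93.8% | 6.63 | 5.31 |
| 2 each | 0.20 | 1.20 | 8.7% | 92.6% | 6.93 | 5.54 |
| Binomial | 0.05 | 1.10 | 4.5% | 93.9% | 6.63 | 5.30 |
| Binomial | 0.10 | 1.20 | 8.5% | 92.7% | 6.92 | 5.53 |
| Binomial | 0.20 | 1.39 | 15.2% | 90.4% | 7.46 | 5.97 |

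Half-widths are in percentage points.

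**Comparisons.** These were simulated with 120 CHWs, a beta-binomial outcome with p = 0.5, a 50:50 binary characteristic, a Pearson chi-square test at 5%, and 20,000 runs.

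| ICC | Characteristic | Type I error, 2 each | Type I error, binomial sizes |
|---|---|---|---|
| 0.10 | varies by woman | 4.8% | 5.0% |
| 0.10 | fixed by CHW | 6.0% | 7.2% |
| 0.20 | varies by woman | 4.7% | 5.2% |
| 0.20 | fixed by CHW | 6.9% | 10.0% |

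A separate simulation at p = 0.7 and ICC 0.10 gave 6.0% and 7.4% for the CHW-level characteristic, and about 5.2% in both settings for the woman-level one.

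**Does the remedy work?** Over ICC 0.05 to 0.20, a cluster-robust interval covered 94.5% to 94.8% at p = 0.5. With the same simulation set-up at ICC 0.10 (equal, then binomial sizes), naive coverage was 93.2% and 92.0% at p = 0.8, against 94.8% and 94.2% cluster-robust. At p = 0.9 it was 92.8% and 91.7%, against 93.9% and 93.5%.

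**The case against.** The strongest reply has four parts.

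1. **Reading of the text.** The section covers two surveys, so it may mean women's characteristics for one and CHWs' characteristics for the other. On that reading few CHW-level comparisons arise in the Women Survey, and comparisons on women's own traits are nearly unaffected. This is fair and limits that half of the point. It leaves the intervals for overall percentages untouched, and women's traits that cluster by locality would still be affected in part.

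2. **Finite population.** The 120 CHWs come from about 700, and all HPV+ women in the arm are surveyed. A correction of 1 − 120/700 = 0.83 would bring the net variance to 0.87, 0.91 and 0.99 of the naive value with 2 women per CHW, and to 0.91, 0.99 and 1.15 with binomial sizes (ICC 0.05, 0.10, 0.20). The naive interval would then be adequate in five of the six cases. This would hold if inference stopped at the current Jujuy CHWs. The section on impact and future directions looks to the wider region and beyond, and Aim 1 applies no such correction.

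3. **Assumed size.** No survey ICC is given, and items about the SMS messages may show little correlation because one central system sends them. This stands.

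4. **Materiality.** An ordinary Wald interval with 240 independent women and p = 0.90 covers only 93.7%, a shortfall similar to that from clustering at ICC 0.10. The effect is indeed small, but the two shortfalls add up: the simulated naive coverage at p = 0.9 was below 93%.

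**Conclusion.** The concern holds, as a minor one. The plan prescribes independence-based methods for women it treats as clustered everywhere else. If within-CHW correlation is positive and inference extends beyond the sampled CHWs, intervals for overall percentages are somewhat too narrow: about 5% at ICC 0.10 with 2 women per CHW, and about 9% if cluster sizes vary binomially. Over the ICC range shown, nominal 95% coverage lies between 90.4% and 94.4%. Any test on a CHW-level characteristic would run at roughly 6% to 7% at ICC 0.10. Woman-level comparisons stay at their nominal level. The direction is well founded, while the size rests on assumed ICCs and cluster sizes. The survey is secondary and mainly descriptive, so the consequence is confined to how its precision is reported. The primary and secondary trial analyses are not affected.

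**What to change.** Add one sentence to Quantitative data analysis, for the Women Survey only: standard errors, 95% confidence intervals and tests, for percentages as well as comparisons, will be clustered on the enrolling CHW, by GEE with a logit link as in Aim 1 or by cluster-robust (survey-design) variance with a design-adjusted chi-square test. The CHW survey can stay as it is, since each CHW responds once.

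The cost is slight. The CHW identifier is already needed for the Aim 1 model, and the list of women to interview is drawn from the same trial database. Intervals widen by 6.63 − 6.33 = 0.30 points of half-width at 50% in the base illustration, and should hardly change if the correlation is near zero.
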